2.4. Participant questionnaires

Participant questionnaires comprise an essential component of any health-related population study. Through questionnaires, we can elicit important health-related information that is not available, is incomplete, or is potentially incorrect in medical records and other health-related linked data that participants consent to donating to Our Future Health when joining the programme. Questionnaire data is also more rapidly obtainable than many health-related linked data and can complement health-record linkage by obtaining repeated measurements or more detailed self-reports than might be possible via the healthcare system. Examples of questionnaire derived health-related information that can supplement and complement health-related linked data include:

- up-to-date health status, exposures, and outcomes (e.g. general health, current cigarette smoker, mental health)
- long-term health or exposure histories that pre-date electronic medical records (e.g. any surgical procedure before 1990, lifetime cigarette smoking history)
- exposures or outcomes that are either poorly or not captured by electronic medical records (e.g. typical alcohol consumption, recent physical activity, over-the-counter medications, mental health)
- Measures that are not regularly repeated or typically available until later in life in medical records (e.g. body weight, alcohol consumption, anxiety, physical activity)
- Health relevant lifestyle factors and personal characteristics that might be unavailable in medical records (e.g. employment status, marital status, type of housing)

³⁶ Wentzensen, N. and R. C. Eldridge (2015). "Invited Commentary: Clinical Utility of Prediction Models for Rare Outcomes-The Example of Pancreatic Cancer." *American Journal of Epidemiology* 182(1): 35-38.

³⁷ Wentzensen, N. and S. Wacholder (2013). "From differences in means between cases and controls to risk stratification: a business plan for biomarker development." *Cancer Discov* 3(2): 148-157.

³⁸ Pepe, M. S., et al. (2008). "Pivotal evaluation of the accuracy of a biomarker used for classification or prediction: standards for study design." *Journal of the National Cancer Institute* 100(20): 1432-1438.

³⁹ Pepe, M. S., et al. (2015). "Improving the quality of biomarker discovery research: the right samples and enough of them." *Cancer Epidemiology, Biomarkers and Prevention* 24(6): 944-950.

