On an average day, how easy do you find getting up in the morning?

SELECT one of 6 from

- 1 Not at all easy
- 2 Not very easy
- 3 Fairly easy
- 4 Very easy
- 1 Do not know
- 3 Prefer not to answer

If this varies a lot, answer this question in relation to the last 4 weeks.

[SL1AB (UKB)]

Do you consider yourself to be?

SELECT one of 6 from

- 1 Definitely a 'morning' person
- 2 More a 'morning' than 'evening' person
- 3 More an 'evening' than a 'morning' person
- 4 Definitely an 'evening' person
- 1 Do not know
- 3 Prefer not to answer

If this varies a lot, answer this question in relation to the last 4 weeks.

[SL1A (UKB)]

Do you have a nap during the day?

SELECT one of 4 from

- 1 Never/rarely
- 2 Sometimes
- 3 Usually
- 3 Prefer not to answer

If this varies a lot, answer this question in relation to the last 4 weeks.

[SL4 (UKB)]

How likely are you to doze off or fall asleep during the daytime when you don't mean to?
(e.g. when working, reading or driving)

SELECT one of 5 from

- 0 Never/rarely
- 1 Sometimes
- 2 Often
- 1 Do not know
- 3 Prefer not to answer

If you are unsure, please provide an estimate or select 'Do not know'.

[SL2 (UKB)]

Do you have trouble falling asleep at night or do you wake up in the middle of the night?

SELECT one of 4 from

- 1 Never/rarely
- 2 Sometimes
- 3 Usually
- 3 Prefer not to answer

If this varies a lot, answer this question in relation to the last 4 weeks.

[SL3 (UKB)]

Does your partner or a close relative or friend complain about your snoring?

SELECT one of 4 from

- 1 Yes
- 2 No
- 1 Do not know
- 3 Prefer not to answer

If you are unsure, please provide an estimate or select 'Do not know'.

[TOBACCO_A (CONNECT)]

Have you ever used any of these **tobacco** products, even once?
Select all that apply.

TOGGLE of 8 choices

[Require ≥1 choices]

- 0 Cigarettes (manufactured or hand-rolled) -> **GO TO S3A**
- 1 Electronic delivery devices that can be vaped, such as e-cigarettes (e.g., UWELL, Vype, Vuse, Vapouriz, WizMix). -> **GO TO V2**
- 2 Cigars, cigarillos, or little filtered cigar (e.g., Montecristo, Romeo Y Julieta, Cohiba, Davidoff, Neos red)

- 3 Chewing tobacco, snus, snuff, Gutkha, or dip (e.g., Skruf, Tulsi, Sikandar, conwood, Al Capone powder)
- 4 Shisha, hookah or water pipe
- 5 Tobacco pipe
- 6 I have **not** used any of these tobacco products **[EXCLUSIVE]** → GO TO S11
- 3 Prefer not to answer **[EXCLUSIVE]**

IF RESPONSE != 0 OR 1 OR 6 GO TO TOBACCO_B

[S3A (CONNECT/UKB)]

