How old were you when you **first** smoked a cigarette?

Enter INTEGER

OR

-1 Do not know

OR

-3 Prefer not to answer

If you do not remember when you had your first cigarette, please enter your best guess.

[V2 (NHS3)]

How old were you when you first used an e-cigarette (vaping)?

Enter INTEGER

OR

-1 Do not know

OR

-3 Prefer not to answer

[V3 (NHS3)]

When you used your first e-cigarette (vaping)

SELECT one of 6 from

- 1 I had never smoked tobacco cigarettes
- 2 I was a current smoker of tobacco cigarettes and had no plans to quit
- 3 I was a current smoker of tobacco cigarettes and was planning to quit
- 4 I was a current smoker of tobacco cigarettes and was planning to reduce smoking
- 5 I had stopped smoking tobacco cigarettes
- 3 Prefer not to answer

[TOBACCO_B (CONNECT)]

Have you ever regularly used any of these **tobacco** products?

Select all that apply.

TOGGLE of 8 choices

[Require ≥1 choices]

- 0 Cigarettes (manufactured or hand-rolled)
- 1 Electronic delivery devices that can be vaped, such as e-cigarettes (e.g., UWELL, Vype, Vuse, Vapouriz, WizMix). → **GO TO V2**
- 2 Cigars, cigarillos, or little filtered cigar (e.g., Montecristo, Romeo Y Julieta, Cohiba, Davidoff, Neos red) → **GO TO S11**
- 3 Chewing tobacco, snus, snuff, **Gutkha**, or dip (e.g., Skruf, Tulsi, Sikandar, conwood, Al Capone powder) → **GO TO S11**
- 4 Shisha, hookah or water pipe → **GO TO S11**
- 5 Tobacco pipe → **GO TO S11**
- 6 I have **not** used any of these tobacco products **[EXCLUSIVE]** → **GO TO S11**
- 3 Prefer not to answer **[EXCLUSIVE]** → **GO TO S11**

We understand that the meaning of "regular basis" might be different for different people. When you answer this question, please think about what "regular basis" means to you.

[S3B (UKB/CONNECT)]

How old were you when you first started smoking **on a regular basis**?

Enter INTEGER

OR

-1 Do not know

OR

-3 Prefer not to answer

We understand that the meaning of "regular basis" might be different for different people. When you answer this question, please think about what "regular basis" means to you.

If you don't know, please give us your best estimate

[S2AA (CONNECT)]

On how many occasions have you smoked cigarettes in your life?

SELECT one of 5 from

- 0 10 or less → **GO TO S11**
- 1 11—49 → **GO TO S11**
- 2 50—99
- 3 100 or more
- 3 Prefer not to answer → **GO TO S11**

[S4(UKB/CONNECT)]

What type of cigarettes have you mainly smoked?

SELECT one of 6 from

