- 1 Manufactured cigarette
- 2 Hand-rolled cigarettes
- 7 None of the above
- 3 Prefer not to answer

If you smoke both hand-rolled, and manufactured cigarettes select the one that you smoke more of.

If you still currently smoke, report the type you smoke most frequently

[S1 (UKB/CONNECT)]

Do you smoke cigarettes now?

SELECT one of 4 from

- 1 Yes, every day
- 2 **Yes, some days**
- 3 **Yes, but rarely**

- 0 No, not at all -> S2 (UKB)
- 3 Prefer not to answer -> S2 (UKB)

[S1A (CONNECT)]

On the days that you smoke, how many cigarettes do you smoke **per day on average**?
Please provide the number of cigarettes, not the number of packs.

Enter INTEGER

OR

-10 Less than one a day

OR

-1 Do not know

→ GO TO S5A

Count the total number of cigarettes (including both hand-rolled and manufactured cigarettes)

For hand-rolled cigarettes:

- One ounce of tobacco makes about 30 cigarettes.
- One gram of tobacco makes about 1 cigarette.

[S2 (UKB/CONNECT)]

In the past, how often have you smoked cigarettes?

SELECT one of 4 from

- 1 Smoked every day -> S2B
- 2 Smoked some days
- 3 Smoked rarely
- 3 Prefer not to answer

[S4AA (UKB/CONNECT)]

Did you ever smoke cigarettes on **most or all days**?

SELECT one of 3 from

- 0 No → GO TO S5A
- 1 Yes
- 3 Prefer not to answer → GO TO S5A

[S4AB (CONNECT)]

On the days that you smoked how many cigarettes did you smoke **per day on average**?
Please provide the number of cigarettes, not the number of packs.

Enter INTEGER

OR

-10 Less than one a day

OR

-1 Do not know

Count the total number of cigarettes (including both hand-rolled and manufactured cigarettes if both are smoked)

For hand-rolled cigarettes:

- One ounce of tobacco makes about 30 cigarettes.
- ONE GRAM OF TOBACCO MAKES ABOUT 1 CIGARETTE.

[S8 (UKB)]

How old were you when you last smoked cigarettes on most days? S11

Enter INTEGER

OR

-1 Do not know

OR

-3 Prefer not to answer

[S5A (UKB)]

Compared to 10 years ago do you smoke...

SELECT one of 4 from

- 1 More nowadays? -> **GO TO S9**
- 2 About the same? -> **GO TO S9**
- 3 Less nowadays? -> **GO TO S5B (UKB)**
- 3 Prefer not to answer -> **GO TO S9**

[S5B (UKB)]

SHOW IF (S5A = 3) OR (S1 > S1A AND S1 != 0 AND S1 != -3)

Why did you reduce your smoking?

(You can select more than one answer)

TOGGLE of 19 choices

[Require ≥1 choices]

- 1 Advice from a GP/Health professional
- 2 TV advert for a nicotine replacement product
- 3 Government TV/radio/Press advert

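### TOBACCO_B has no answer for use that was never regular, and its routing leaves cigarette users who claim no regular use without a lifetime count or current-smoking status

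*Protocol*

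**What the plan says.** All items are in Protocol, Appendix E, Section 3 (Your lifestyle).

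- **TOBACCO_A** asks "Have you ever used any of these tobacco products, even once". Respondents who report no use go straight to S11, the item on other people's smoke.
- **TOBACCO_B** then asks "Have you ever regularly used any of these tobacco products". It carries the rule "Require ≥1 choices". The answers are products 0 to 5, option 6, and a refusal. Option 6 reads "I have not used any of these tobacco products [EXCLUSIVE] → GO TO S11".
- **Help text at TOBACCO_B** says: "When you answer this question, please think about what 'regular basis' means to you".
- **S2AA**, after TOBACCO_B, asks "On how many occasions have you smoked cigarettes in your life". The two lowest categories (10 or less, 11 to 49) and refusal go to S11. The two categories from 50 upwards continue.
- **S1**, after S2AA, asks "Do you smoke cigarettes now". Its answers include smoking on some days and smoking rarely.

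Section 2.4 lists what the questionnaire is meant to add to linked records, including "up-to-date health status, exposures, and outcomes (e.g. general health, current cigarette smoker, mental health". In the same list it gives lifetime cigarette smoking history as an example of exposure that pre-dates electronic records.

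**The concern.** There are two linked faults.

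First, the stem of TOBACCO_B is about regular use but its 'none' option is about any use; the wording has been carried over from TOBACCO_A. A person who tried a product and never used it regularly must deny use already reported, claim regular use, or refuse.

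Second, the answer decides whether the two basic cigarette items are asked at all. The deciding word, regular, has no fixed meaning. Two people with the same smoking pattern can be routed differently: one gets a count and a current status, the other gets neither. The gaps then depend on how people see their own smoking rather than on how much they smoke, and an analysis cannot restore answers that were never requested.

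The fault may also spread. Section 3.7 says the short questionnaire will be drawn from the approved questions without new items.

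**Working it through.** No stated figure is at issue, so the check follows the printed routes. Inputs are the answer lists and jumps from TOBACCO_A to the start of the alcohol items. An answer with no printed jump is taken to fall through to the next printed item.

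**Step 1: who sees TOBACCO_B.** TOBACCO_A option 6 leaves for S11. Cigarette users go to S3A (age at first cigarette) and on through V2 and V3. Users of other products go directly or by way of V2. Apart from people who refused TOBACCO_A, everyone who arrives has reported some use, so option 6 at TOBACCO_B is literally untrue for all of them.

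**Step 2: where each TOBACCO_B answer leads.**

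| TOBACCO_B answer | Next item | Can reach S2AA | Can reach S1 |
|---|---|---|---|
| 0 cigarettes | S3B | yes | yes, if S2AA is 50 or more |
| 1 e-cigarettes | V2, then V3, then TOBACCO_B again | no | no |
| 2 to 5 other products | S11 | no | no |
| 6 none | S11 | no | no |
| Refusal | S11 | no | no |

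One of the eight answers leads to S2AA and S1. With TOBACCO_B removed from the map, neither item can be reached from TOBACCO_A, so there is no way round it.

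**Step 3: can the missing values be found elsewhere in the questionnaire?** S3A gives age at first cigarette only. V3 gives smoking status at the first vape, for vapers only. S11 and S12 concern other people's smoke. None gives current smoking or a lifetime count.

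**Step 4: the second filter.** Among people who tick cigarettes at TOBACCO_B, S2AA answers below 50 occasions also jump to S11 before S1. Rewording TOBACCO_B alone would not give those people a current-smoking value.

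**Step 5: size.** The protocol states no prevalence of ever, regular or occasional smoking, so the number cannot be calculated. As a scale only: 0.01 × 5,000,000 = 50,000 people for each 1% of the target cohort who used cigarettes but do not tick option 0.

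**The case against.** Several points on the other side are sound and limit the finding.

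- **A reader might infer that current occasional smokers never reach S1.** The routes do not support that. TOBACCO_B asks about ever regular use. An occasional smoker who once smoked regularly, or who calls present use regular, ticks option 0 and reaches S1 if reporting 50 or more occasions.
- **A reader might infer that the light-use answers at S1 and S2AA have nobody left to use them.** They do: former regular smokers who have cut down, and people who ticked option 0 under a loose meaning of regular.
- **Not every missing S1 value is due to TOBACCO_B.** S2AA excludes people on its own account.
- **The missing 'none' can partly be repaired in analysis.** A product ticked at TOBACCO_A with option 6 at TOBACCO_B most sensibly means used, not regularly. That recovers regular-use status for people who answer this way. It does not recover S1 or S2AA.
- **A reader might want a rate of false regular users of cigars, shisha, pipe or smokeless tobacco.** The protocol offers nothing to base one on. Assumptions about cigarette triers do not carry over to those products, and for cigarettes S2AA gives a partial check.
- **Those routed out are not indistinguishable from one another.** S3A still records age at first cigarette.
- **Self-defined regularity looks deliberate.** The help text appears at both TOBACCO_B and S3B, and Section 3.6 reports cognitive testing, piloting and Scientific Advisory Board review. As a way of asking about regular use it is defensible. It becomes a problem only because it decides who is asked S2AA and S1.
- **Linked primary care data may hold some smoking information.** Section 2.4 nevertheless justifies the questionnaire on the ground that such records can be unavailable, incomplete or incorrect.

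None of this removes the core: the contradictory option, and the absence of both values for cigarette users who do not claim regular use.

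**Conclusion.** The point holds in this form. TOBACCO_B offers no true answer to people who used tobacco but never regularly. Cigarette users who have never smoked regularly by their own definition, some of whom smoke occasionally now, finish the questionnaire without a lifetime count or a current-smoking status. Section 2.4 gives current smoking and lifetime smoking history as examples of what the questionnaire should supply.

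The conclusion rests on the printed answer lists and jumps, with unrouted answers taken to fall through to the next item. It does not depend on how respondents read option 6, because that option goes to S11 under either reading. The number affected is unknown. The change should be made because the loss cannot be repaired in analysis and the correction is small; the finding does not put the wider programme in doubt.

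**What to change.** 1. Reword TOBACCO_B option 6 to: *I have not used any of these regularly.*
2. Ask S1 and S2AA of everyone who ticked cigarettes at TOBACCO_A, before TOBACCO_B.
3. At that new position, remove their present jumps (S2AA to S11; S1 to S2 or on to S1A) so that everyone continues to TOBACCO_B. If the jumps were kept, light cigarette smokers would skip TOBACCO_B and lose any record of regular cigar, shisha, pipe or smokeless use, and both current smokers and non-smokers would bypass TOBACCO_B and S3B.
4. Apply the 50-occasion filter, and the branch from S1 to S1A or S2, only after TOBACCO_B option 0, where they control the detailed items (S3B, S4, S1A onward).

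The cost is one reworded option, two short extra questions for people who only tried cigarettes, and a small routing change to be tested before release. The self-defined meaning of regular can stay, since it would then control only the detailed items.

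### The baseline questionnaire does not ask current 'some days' and 'rarely' smokers whether, how heavily or until when they once smoked on most days, so lifetime exposure cannot be derived for those who cut down

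*Protocol*

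**What the plan says.** The items are in Protocol Appendix E, Section 3 (Your lifestyle).

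- S1 asks "Do you smoke cigarettes now". Its three yes answers (1 every day, 2 some days, 3 rarely) carry no routing instruction, so they fall through to the next item, S1A. Only "No, not at all -> S2 (UKB") and the refusal option are sent to S2.
- S1A asks how many cigarettes are smoked on the days the person smokes, and then exits to S5A.
- The items between S1A and S5A are S2 ("In the past, how often have you smoked cigarettes"), S4AA ("Did you ever smoke cigarettes on most or all days"), S4AB ("On the days that you smoked how many cigarettes did you smoke") and S8 ("How old were you when you last smoked cigarettes on most days").
- At S4AA, no and refusal go to S5A; yes continues to S4AB and then S8. The S8 line ends with a bare S11 and no arrow.

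Section 2.4 lists "lifetime cigarette smoking history" among the examples of long-term histories that predate electronic records and that a questionnaire can supply. Section 3.6 says the baseline questionnaire is meant to capture factors that linkage would not, or not easily, provide.

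**The concern.** A person can smoke a pack a day for decades and now smoke only occasionally. On the printed route the baseline form records the present amount for that person but not the daily phase that makes up most of the exposure. Someone who refuses S1 is asked more about past smoking than someone who admits to occasional smoking.

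The instrument already recognises the need. A former smoker who reports at S2 having smoked on some days or rarely is carried on to S4AA, which picks up an earlier daily phase. Current occasional smokers need the same check and do not get it.

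If analysts fill the gap with current amount and start age, former heavy daily smokers would be placed among people with low exposure. Smoking dose-response estimates would be distorted, and residual confounding could remain where smoking is an adjustment variable. An analysis plan cannot repair this, because the data are not collected.

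**Working it through.** The protocol states no smoking amounts and no exposure formula, so there is no figure of its own to reproduce. The check has three parts: trace the routing, ask whether other items recover the information, and illustrate the size on assumed people.

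**1. Routing, for a cigarette smoker who reaches S1**

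- S1 = 1, 2 or 3: S3A, TOBACCO_B, S3B, S2AA, S4, S1, S1A, S5A, (S5B), S9.
- S1 = 0 or refusal: the same up to S1, then S2 and S4AA and, if yes, S4AB and S8. This leaves aside the separate S2B target printed at S2 for past daily smokers; repairing it would not help the present group, who never reach S2.

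**2. What the items that are asked can tell us**

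- S3A and S3B: ages at first cigarette and at start of regular smoking. No amount, no end.
- TOBACCO_B: ever used regularly, with the meaning of regular left to the respondent.
- S2AA: lifetime occasions, with a top category of 100 or more.
- S5A: more, the same or less than 10 years ago. Direction only. Someone who cut down 12 years ago can truthfully answer about the same.
- S5B: why the person reduced, not from what amount or when.
- S9: whether the person ever stopped for more than 6 months.

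None gives past smoking on most days, past cigarettes per day, or the age at which daily smoking ended.

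**3. Illustration**

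All values are assumed: age 60, regular smoking from 18, daily amount X until age q, then c cigarettes per smoking day on 3 days a week.

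- True pack-years = (q − 18) × X/20 + (60 − q) × c × (3/7)/20
- Unweighted proxy from S1A and S3B = 42 × c/20
- Weighted proxy = 42 × c × (3/7)/20. The weight is itself an assumption, since S1 records only 'some days' or 'rarely'.

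| Person | True | Unweighted | Weighted |
|---|---|---|---|
| (a) 20/day to 48, now 2 | 30 + 0.5 = 30.5 | 4.2 (14%) | 1.8 (6%) |
| (b) 20/day to 55, now 5 | 37 + 0.5 = 37.5 | 10.5 (28%) | 4.5 (12%) |
| (c) 10/day to 30, now 5 | 6 + 3.2 = 9.2 | 10.5 (114%) | 4.5 (49%) |
| (d) never daily, always 3 | 2.7 | 6.3 (233%) | 2.7 (100%) |

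The shortfall is large for those who cut down from heavy daily use. It depends on the formula for (c), and is absent or reversed for (d).

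With S4AB and S8 available, the daily phase is S4AB/20 × (S8 − S3B). For (a) this is 20/20 × (48 − 18) = 30 of the 30.5 true pack-years; for (b) it is 20/20 × (55 − 18) = 37 of 37.5.

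**The case against.** The strongest reply is that the gap is narrower than it first looks. A reader might infer that current occasional smokers are asked nothing about the past. That is not so: they answer S3A, TOBACCO_B, S3B, S2AA, S5A (with S5B if they smoke less) and S9. Four items are missed, not all of them. S5A flags people who reduced within about 10 years, and S5B lets them name health problems as the reason, which helps with reverse causation. Person (b), who cut down 5 years ago, would be flagged; person (a), 12 years ago, need not be. But the flag carries no amount and no date, so it identifies some of those affected without allowing their exposure to be calculated.

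A reader might also infer that the plan grossly understates lifetime exposure for this whole group. The documents do not support that. They define no pack-year measure, S1A is worded as current intensity, and persons (c) and (d) show that the error can vanish or reverse. The data are missing rather than falsely recorded.

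Finally, Section 2.4 gives smoking history as an example, not as a promise of a complete quantified record in this form, and the protocol allows for later questionnaires and recontact. The gap could be filled later, but nothing in the protocol commits to doing so, and Section 3.7 draws the short questionnaire from the same items.

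**Conclusion.** The point stands in limited form. On the printed routing, past frequency, past daily amount and the end of daily smoking are not collected from current 'some days' and 'rarely' smokers, and no other baseline item supplies them. Lifetime exposure cannot be derived for those in this group who once smoked on most days. An exposure built from S1A and start age would understate it for those who cut down from heavier daily smoking, by an amount that depends on the formula: 6% to 28% of the true value is recorded in the two assumed 20-a-day cases.

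The number of people affected cannot be taken from the protocol. Each 1% of a 5 million cohort is 50,000 people, so an assumed share of 1% to 3% would mean 50,000 to 150,000, but nothing in the document supports any particular share. The size of any resulting bias in disease associations has not been calculated.

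Current daily smokers bypass the same four items, so an earlier, different daily amount is lost for them too. The change below does not address that.

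**What to change.** Replace the exit of S1A with: IF S1 = 1 GO TO S5A; IF S1 = 2 or 3 GO TO S4AA. Keep S4AA no and refusal going to S5A. State that for this group a yes at S4AA leads to S4AB, S4AB leads to S8, and S8 exits to S5A.

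The last part matters. If the S11 printed at S8 is read as its exit, the rerouted former daily smokers would lose S5A, S5B and S9, which they now answer. That S11 should be replaced or clarified in the same edit.

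The cost is a small routing change using items already in the questionnaire: one extra question for current occasional smokers, and two more for those who once smoked on most days.

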- 4 Hearing about a new stop smoking treatment
- 5 A decision that smoking was too expensive
- 6 Being faced with smoking restrictions
- 7 I knew someone else who was stopping
- 8 Seeing a health warning on a cigarette pack
- 9 Being contacted by my local NHS Stop Smoking Services
- 10 Health problems I had at the time
- 11 A concern about future health problems
- 12 Attending a local stop smoking activity or event
- 13 Something said by family/friends/children
- 14 A significant birthday
- 15 The coronavirus outbreak
- 16 Restrictions on where I could smoke

- 7 None of the above [**EXCLUSIVE**]
- 1 Do not know [**EXCLUSIVE**]
- 3 Prefer not to answer [**EXCLUSIVE**]

→ GO TO S9

[S9 (UKB)]

In the time that you smoked, did you ever stop for more than 6 months?

SELECT one of 4 from

- 1 Yes -> **GO TO S10**
- 0 No -> **IF (S1 == 0 AND S3 != -3) GO TO S10 ELSE GO TO S11**
- 1 Do not know -> **IF (S1 == 0 AND S3 != -3) GO TO S10 ELSE GO TO S11**
- 3 Prefer not to answer -> **IF (S1 == 0 AND S3 != -3) GO TO S10 ELSE GO TO S11**

[S10 (TOOLKIT)]

Why did you stop smoking?
(You can select more than one answer)

TOGGLE of 19 choices

[Require ≥1 choices]

- 1 Advice from a GP/Health professional
- 1 TV advert for a nicotine replacement product
- 1 Government TV/radio/Press advert
- 1 Hearing about a new stop smoking treatment
- 5 A decision that smoking was too expensive
- 6 Being faced with smoking restrictions
- 7 I knew someone else who was stopping
- 8 Seeing a health warning on a cigarette pack
- 9 Being contacted by my local NHS Stop Smoking Services
- 10 Health problems I had at the time
- 11 A concern about future health problems
- 12 Attending a local stop smoking activity or event
- 13 Something said by family/friends/children
- 14 A significant birthday
- 15 The coronavirus outbreak
- 16 Restrictions on where I could smoke

- 7 None of the above **[EXCLUSIVE]**
- 1 Do not know **[EXCLUSIVE]**
- 3 Prefer not to answer **[EXCLUSIVE]**

[V4 (NHS3)]

How often, on average, did you use e-cigarettes (vaping) during the past 12 months?

SELECT one from 12

- 1 Never
- 2 Less than 1 time/mo
- 3 2-3 times/mo
- 4 1-2 times /week
- 5 3-6 times /week
- 6 1-4 times /day
- 7 5-14 times /day
- 8 15-24 times /day
- 9 25– 34 times /day
- 10 35 – 44 times /day
- 11 More than 45 times /day
- 3 Prefer not to answer

[V5 (NHS3)]

What type of e-liquids/cartridges do you or did you use in your e-cigarettes?

CHOOSE ALL THAT APPLY

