- 1 Fruit/dessert flavour WITHOUT nicotine
- 2 Fruit/dessert flavour WITH nicotine
- 3 Menthol flavour WITHOUT nicotine
- 4 Menthol flavour WITH nicotine
- 5 Tobacco flavour WITHOUT nicotine
- 6 Tobacco flavour WITH nicotine
- 7 Marijuana or THC concentrate
- 8 Alcohol
- 9 Other:
- 3 Prefer not to answer

[S11V2 (CONNECT)]

In **the past year**, about how often were you around tobacco smoke from other people smoking in your home or at work?

SELECT one of 8 from

- 1 Every day
- 1 Most days of the week
- 2 A few days per week
- 3 One day per
- 4 A few days per month
- 5 One day per month
- 6 A few days per
- 0 Never → **GO TO A1**
- 3 Prefer not to answer → **GO TO A1**

[S12 (UKB)]

On days you were around other people's tobacco smoke in **the past year** in your home or work, about how many hours per day were you around it?

SELECT one of 6 from

- 0 Less than 1 hour per day
- 1 1 to 2 hours per day
- 2 3 to 5 hours per day
- 3 6 to 9 hours per day
- 4 10 to 15 hours per day
- 5 More than 15 hours per day
- 3 Prefer not to answer

IF TOBACCO _B = 1 GO TO V2 ELSE GO TO A1

[A1 (UKB)]

About how often do you drink alcohol?

SELECT one of 7 from

- 1 Daily or almost daily
- 2 Three or four times a week
- 3 Once or twice a week
- 4 One to three times a month -> GO TO A2B (UKB)
- 5 Special occasions only -> GO TO A2B (UKB)
- 6 Never -> GO TO A1A (UKB)
- 3 Prefer not to answer -> GO TO END SECTION 3

If this varies a lot, please provide an average considering your intake over the last year

[A1A (UKB)]

Did you previously drink alcohol?

SELECT one of 3 from

- 1 Yes -> GO TO A7A (UKB)
- 0 No -> GO TO END SECTION 3
- 3 Prefer not to answer -> GO TO END SECTION 3

[A2B (UKB)]

In an average MONTH, how many glasses of RED wine would you drink?
(There are six glasses in an average bottle)

Enter INTEGER

OR

- 1 Do not know

OR

- 3 Prefer not to answer

Please include sparkling red wine here.

[A2C (UKB)]

In an average MONTH, how many glasses of WHITE wine or champagne would you drink?
(There are six glasses in an average bottle)

Enter INTEGER

OR

-1 Do not know

OR

-3 Prefer not to answer

Please include sparkling white wine, prosecco and rosé here.

[A2E (UKB)]

In an average MONTH, how many pints of beer or cider would you drink?
(Include bitter, lager, stout, ale, Guinness)

Enter INTEGER

OR

-1 Do not know

OR

-3 Prefer not to answer

[A2A (UKB)]

In an average MONTH, how many measures of spirits or liqueurs would you drink?

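### Followed as printed, Appendix E's tobacco routing misses cigarettes per day and quit age for former daily smokers, and vaping frequency for exclusive vapers

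*Protocol*

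**What the plan says.** All of this is in Appendix E, Section 3 of the questionnaire (Your lifestyle).

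- **Former smokers.** At S1, people who do not smoke now, or who decline to answer, go to S2. There the every-day answer is printed "Smoked every day -> S2B". The some-days and rarely answers carry no jump, so they run on to S4AA ("Did you ever smoke cigarettes on" most or all days). Yes at S4AA continues to S4AB ("On the days that you smoked how many cigarettes did you smoke" per day) and then S8 ("How old were you when you last smoked cigarettes on most days"). A loose S11 stands at the end of S8.
- **Vapers.** TOBACCO_B, a select-all item on regular use, sends its e-cigarette option back to V2. After S12 the rule is "IF TOBACCO _B = 1 GO TO V2 ELSE GO TO A1".
- **Vaping detail.** V4 ("How often, on average, did you use e-cigarettes (vaping) during the past 12 months") and V5 (liquid type) are printed directly after S10, which asks why the respondent stopped smoking.
- **S9.** For answers other than Yes the routing is "IF (S1 == 0 AND S3 != -3) GO TO S10 ELSE GO TO S11".

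Section 2.4 gives lifetime cigarette smoking history as an example of what the questionnaire must supply because records do not. Section 3.6 says the questionnaire is for factors that linkage cannot readily provide.

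**The concern.** Pack-years and time since quitting need start age, amount and stop age. For former smokers the last two come only from S4AB and S8. If people who smoked every day bypass both items while lighter former smokers answer them, the missingness follows past exposure, and any later analysis that adjusts for smoking inherits it. For e-cigarettes, frequency and liquid type would be missing for people who vape and have never smoked, the group in whom vaping can be studied without the effect of smoking.

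**Working it through.** No sample-size or power figure is involved. The check is a trace of the routing.

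**1. Labels.** The tobacco block prints 22 items in this order: TOBACCO_A, S3A, V2, V3, TOBACCO_B, S3B, S2AA, S4, S1, S1A, S2, S4AA, S4AB, S8, S5A, S5B, S9, S10, V4, V5, S11V2, S12. Three labels are used in jumps or conditions but not defined: S2B, S3 (only S3A and S3B exist) and S11 (printed as S11V2). S11 plainly means S11V2. The other two have no such reading.

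**2. Trace by respondent type.** Jumps are followed as printed, S11 is read as S11V2, and the loose S11 at S8 is ignored.

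| Respondent | Path | S1A | S4AB | S8 | V4 |
|---|---|---|---|---|---|
| Former daily smoker, no vaping | S3A, V2, V3, TOBACCO_B, S3B, S2AA, S4, S1, S2, then S2B (undefined) | no | no | no | no |
| Former some-days smoker, S4AA = Yes, S9 = Yes | as above to S2, then S4AA, S4AB, S8, S5A, S9, S10, V4, V5, S11V2, S12, A1 | no | yes | yes | yes |
| Current daily smoker, never stopped | as above to S1, then S1A, S5A, S9, S11V2, S12, A1 | yes | no | no | no |
| Regular vaper only | V2, V3, TOBACCO_B, V2, V3, TOBACCO_B, … without end | no | no | no | no |
| Ever but not regular vaper only | V2, V3, TOBACCO_B, S11V2, S12, A1 | no | no | no | no |

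**3. Reading the table.** No instruction names S4AB, S8, V4 or V5 as a target; they are reached only in printed sequence. Former some-days smokers who do not vape are shown V4 and V5, while exclusive vapers, regular or not, are not.

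**4. Alternative handling of S2B.** If the undefined target is ignored and the respondent runs on to the next printed item, a former daily smoker goes S2, S4AA, S4AB, S8, and both amount and quit age are collected. This does not cure the vaping loop or give exclusive vapers a route to V4.

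**5. The loose S11.** If it is read as a jump, everyone who reaches S8 goes straight to S11V2 and skips S5A, S9, S10, V4 and V5.

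**6. S9.** Because S3 is undefined, it is unclear whether a former smoker who does not answer Yes goes to S10 or to S11. This decides who is asked reasons for stopping and, by sequence, who sees V4 and V5.

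**The case against.** **The loss is conditional.** This is the strongest point on the other side, and it stands. A jump to a missing item cannot be executed, and the document does not say what the software then does. Step 4 shows that a fall-through recovers both cigarette items. Still, S4AA is redundant for someone who has just said they smoked every day, so the jump looks meant to skip it, and nothing in the document specifies the fall-through.

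**Appendix E is not the whole build specification.** It defers to a spreadsheet for some response lists, and section 10.2.1 expects the platform to be customised from a procured system. That limits what can be said about the live build, not about the printed routing.

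**The pilot worked.** Section 3.6 reports complete questionnaires from over 1,500 people and 95% completion among those who started. That was the initial version; Appendix E holds the revised one. The sections named as expanded are health and family history, so the pilot neither clears nor condemns the tobacco block. Completion also does not show that a given item was reached.

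**Gaps can be repaired later.** Repeat questionnaires are planned (section 2.4) and the consent allows re-contact (section 3.5). Start age, the lifetime-occasions band, cigarette type and past frequency are still collected from former daily smokers who do not vape regularly. This reduces the harm but does not make the routing right.

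**Stronger readings that do not hold.** A reader might infer that smoking data are lost in all heavily exposed groups, but current smokers give their amount at S1A. A reader might infer that every vaper loops, but only those ticking e-cigarettes at TOBACCO_B do. A reader might infer that e-cigarette exposure is recorded in the wrong people, but V4 offers a never option, so a non-vaper shown it can answer correctly. The odd display rule at S5B, which compares a frequency code with a cigarette count, has no effect: only S5A = 3 leads to S5B, and that alone satisfies the rule.

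**Conclusion.** The tobacco routing is wrong as printed, and the fault is more than clerical. Followed literally, it omits cigarettes per day and quit age for former daily smokers, traps regular vapers in a loop, and leaves exclusive vapers without frequency or liquid type. The vaping faults hold however S2B is handled; the cigarette loss holds only if the build does not fall through to S4AA.

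The number of people affected cannot be given. A reader might multiply an assumed share of former daily smokers by 5 million, but the document gives no such share, and the result would also assume an uncorrected live build. The conclusion needs neither.

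**What to change.** In Appendix E:

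1. Route S2 = 1 to S4AB, and remove the loose S11 at S8.
2. Show V2 and V3 only if e-cigarettes are ticked in TOBACCO_A, and remove the jump to V2 at TOBACCO_B = 1.
3. After TOBACCO_B, send anyone who ticked cigarettes to S3B and the cigarette items first; everyone else goes to the gate in step 4.
4. Point every exit to S11, and the end of S10, to one gate: if e-cigarettes are ticked in TOBACCO_A or TOBACCO_B, show V4 and V5 and then S11V2; otherwise go to S11V2.
5. Delete the check after S12, so that S12 leads to A1.
6. In the S9 condition, replace S3 with S2.
7. Check the live build against the corrected routing.

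Two shorter repairs should be avoided. Pointing the check after S12 to V4 makes a new loop (V4, V5, S11V2, S12, V4). Sending every TOBACCO_B = 1 respondent straight to V4 and on to S11V2 skips the cigarette items for people who regularly both smoked and vaped.

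Under steps 1 to 6 a former daily smoker goes S2, S4AB, S8, S5A, S9 and on to the gate. A regular vaper only goes V2, V3, TOBACCO_B, gate, V4, V5, S11V2, and then S12 and A1, or directly A1 where S11V2 already exits. A dual user completes the cigarette items before V4. The cost is routing edits and one test of the build, with no new items.
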